15.2.3 Pharmacokinetic Amounts Excreted

Urinary and fecal TR PK parameters will be calculated using SAS. Excretions in mg equivalent (mg eq) and % of dose for each interval ($Ae_{t_{1-2}}$) will be derived from the urinary and fecal concentrations and the sample collection interval volumes or weights respectively, by multiplying the concentration in the interval (C) and the volume or weight (V):

$$Ae_{t_{1-2}} = C \times V$$

If the concentration is <LLOQ the excretion will be assumed to be zero. For intervals in which no sample was collected (e.g., no defecation), the excretion will be assumed to be zero. If needed, for cumulative excretions, the last observation carried forward (LOCF) method will be used up to the last time point.

Cumulative excretions for each continuously sampled interval will be calculated by summarizing the excretions in the current and all previous collection intervals:

$$Ae_{0-t} = \sum_{i=1}^n (Ae_{t_{start}-t_{end}})_i$$

For subjects with an incomplete mass balance on Day 8, the cumulative excretion up to each interval (Day 12 and Day 16) will be supplemented by estimating the area under the excretion rate versus time curve (AURC) for intervals between the in house period and ambulant visits.

The excretion rate ($\Delta Ae / \Delta t$) will be calculated by dividing the excretion in each interval by the time difference in hours between the end and the start of the collection interval:

$$\Delta Ae / \Delta t = \frac{Ae}{t_{end} - t_{start}}$$

Ae_{urine} and Fe_{urine} : Descriptive statistics (number of subjects, arithmetic mean, standard deviation, coefficient of variation) will be used to summarize the urine amounts excreted as TR, BTZ-043 (M0), M1, M2, M4_{total}, M10, and $\Sigma(M0, M1, M2, M4_{total}, M10)$ by the 4 subjects for each day pool, as well as for the total collection periods. No statistics will be available for the urine amounts excreted as individual 'other metabolites' due to the pooled analysis of the radio-profile. The same holds true for the overall sum of excreted amounts of metabolites in urine.

Ae_{feces} and Fe_{feces} : Descriptive statistics (number of subjects, arithmetic mean, standard deviation, coefficient of variation) will be used to summarize the feces amounts excreted as TR by the 4 subjects for

each day pool, as well as for the total collection periods. No statistics will be available for the feces amounts excreted as BTZ-043 (M0), M1, M2, M4_{total}, M10 and individual 'other metabolites' due to the pooled analysis of the radio-profile. The same holds true for the sum of excreted amounts of metabolites.

A_e_{total} and F_e_{total}: Descriptive statistics (number of subjects, arithmetic mean, standard deviation, coefficient of variation) will be used to summarize the overall excreted amounts of TR by urine, feces (and vomitus, if applicable) of the 4 subjects over the total collection period. No statistics will be available for the overall excreted amounts of BTZ-043 (M0), M1, M2, M4_{total}, M10, individual 'other metabolites' and overall sum of metabolites.

Linear plots of the cumulative TR (Fe) in urine, feces and total amounts excreted per day pool will be provided by subject and as mean over 4 subjects. These plots will show time in hours.

Individual total radioactivity excretion data (concentrations, volumes, weights, amount excreted and excretion rate [if applicable]) will be listed per collection interval.

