In the event of an incomplete mass balance on the morning of Day 8, subjects may be discharged from the clinical site upon discretion of the Investigator. Subjects with an incomplete mass balance (<90% of dose administered and/or combined urinary and fecal excretion >1% of the administered dose per 24 hours for 2 consecutive days based on C-radioactivity "quick counts" or normal counts, as feasible) on Day 8 will be asked to return to the clinical site for one or two 24-hour visits (Day 11-12 and Day 15-16).

In the event of subjects not defecating for 2 days, measures will be taken to ensure defecation (eg, additional fibers, plum juice, dried prunes, and/or sufficient hydration).

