### **3.5.1.1.3 Feces Collection**

During the intervals defined in the schedule of assessments, all fecal excretions will be collected for the analysis of total radioactivity, for quick or normal counts of total radioactivity (as feasible), and for metabolite profiling and identification. A blank fecal sample will be collected within 48 hours prior to study drug administration. The exact times of feces collection and the fecal weight will be recorded in the eCRF.

Details on sample collection, handling, storage, and shipping will be described in the laboratory manual prepared by PRA and Nuvisan.

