- b Subjects will be released from the clinic 96 hours after dose administration and upon satisfactory recovery of radioactivity.
- c Complete physical examinations will be conducted at screening, Day -1, and follow-up/early termination. Symptom driven physical examinations may be conducted at any time, per the Investigator's discretion.
- d Sampling of nasal and throat mucosal cells. If deemed necessary, additional tests may be conducted during the study. The nonclinical project manager will be informed immediately upon availability of Day 11 results, as this will qualify the feces samples for metabolite profiling with regard to potential COVID-19 infectivity.
- e Clinical laboratory tests (including clinical chemistry, hematology, and urinalysis): at screening; on Day -1 (admission), Day 2, and Day 4; and at follow-up.
- f 12-lead ECG: at screening; Day -1, and 1 hour, 4 hours, and 24 hours postdose; at discharge; and at follow-up.
- g Vital signs (supine systolic and diastolic blood pressure, pulse, body temperature, and respiratory rate): at screening; at admission; at predose and at 1 hour, 4 hours, and 24 hours postdose; at discharge; and at follow-up.
- h Plasma sampling for PK of BTZ-043 and main metabolites in plasma: at predose and 0.25, 0.5, 1, 1.5, 2, 3, 5, 8, 12, 16, 24, 36, and 48 hours postdose.
- i Total radioactivity in whole blood and plasma: at predose and 0.25, 0.5, 1, 1.5, 2, 3, 5, 8, 12, 16, 24, 36, 48, 72, and 96 hours postdose (in case total radioactivity recovered is still <90%: in addition 120, 144, and 168 hours postdose and at further 24-hour visits [264 and 360 hours postdose] until study completion). Metabolite profiling in plasma: at predose and 0.25, 0.5, 1, 1.5, 2, 3, 5, 8, 12, 16, 24, 36, 48, 72, and 96 hours postdose (in case total radioactivity recovered is still <90%: in addition 120, 144, and 168 hours postdose. Metabolite profiling in plasma: at predose and 0.25, 0.5, 1, 1.5, 2, 3, 5, 8, 12, 16, 24, 36, 48, 72, and 96 hours postdose (in case total radioactivity recovered is still <90%: in addition 120, 144, and 168 hours postdose).

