- j Urine collection and pooling for BTZ-043 and main metabolites, total radioactivity, and metabolite profiling: at predose (within 12 hours prior to dosing) and over 0-24, 24-48, 48-72, and 72-96 hours postdose collection intervals (in case total radioactivity recovered is still <90%, in addition 96-120, 120-144, and 144-168 hours postdose and at further 24-hour intervals [Day 11-12 and Day 15-16] until study completion).
- k Feces collection for total radioactivity and metabolite profiling; predose feces collection to be collected at any time within 48 hours prior to study drug administration (at home or in the clinic). After administration of BTZ-043, feces will be collected in 24 hour collection intervals up to 96 hours postdose (in case total radioactivity recovered is still <90%: in addition 120, 144, and 168 hours postdose and at further 24-hour intervals [Day 11-12 and Day 15-16] until study completion).
- l If produced, vomit will be collected up to 8 hours after the administration of the study drug for total radioactivity determination.
- m Day 6-8 procedures will only be conducted in case that the recovery of radioactivity was not satisfactory until Day 5. 24-hour visits procedures will only be conducted in case that the recovery of radioactivity was not satisfactory until Day 8. For the 24-hour visits (if applicable): feces collection to be collected at home within 48 hours prior to admission.

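### SAP 15.2.3 applies a urine-type excretion rate to feces, so at the edge of an uncollected gap a stool-less day or a backlog stool moves a recalled subject's AURC supplement by about half

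*SAP*

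**What the plan says.** SAP 15.2.3 combines three rules.

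- **Rate.** One formula, Ae/(t_end − t_start), serves urine and feces: "dividing the excretion in each interval by the time difference in hours between the end and the start of the collection interval".
- **Zero rule.** "For intervals in which no sample was collected (e.g., no defecation), the excretion will be assumed to be zero".
- **Gap filling.** For subjects incomplete on Day 8, the cumulative amount up to Day 12 and Day 16 is "supplemented by estimating the area under the excretion rate versus time curve (AURC) for intervals between the in house period and ambulant visits".

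The interval lengths come from the schedule in SAP Appendix 2. Footnote k says "feces will be collected in 24 hour collection intervals up to 96 hours postdose", with further windows ending at 120, 144 and 168 h if recovery is short. Footnote i fixes the return-visit clock for blood: "at further 24-hour visits [264 and 360 hours postdose] until study completion". Footnote m adds: "For the 24-hour visits (if applicable): feces collection to be collected at home within 48 hours prior to admission".

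The Protocol bears on stool frequency in two places. Exclusion Criterion 3 bars men who average fewer than one stool a day, and the Synopsis says: "In the event of subjects not defecating for 2 days, measures will be taken to ensure defecation". Protocol 3.5.1.1.3 adds: "The exact times of feces collection and the fecal weight will be recorded in the eCRF".

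The SAP does not name an integration rule for the AURC. It does not define t_start and t_end for the home stool, or say whether that stool belongs to the visit interval.

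**The concern.** Urine forms continuously, so amount over interval length is a fair rate. A stool carries everything accumulated since the one before it, so its radioactivity divided by the length of the window in which it fell is not a rate of fecal excretion.

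Within the in-house period this does no harm: a missed day is made up by the next collected stool and the cumulative sum is right. At the edge of a gap it does harm, because the stool that carries the backlog may never be collected. A stool-less 144–168 h window becomes a rate of 0, a stool after one stool-less day becomes about twice the true rate, and that single value is spread across the gap.

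The supplement enters cumulative excretion, and so Fe(feces) and Fe(total), which serve the first primary objective. It applies to exactly the subjects whose recovery is incomplete, and results are summarised over 4 subjects.

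**Working it through.** The plan gives no numerical AURC result, so there is no figure to reproduce.

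**1. Gap length.** Hours = (day − 1) × 24. Day 8 = 168, Day 11 = 240, Day 12 = 264, Day 15 = 336, Day 16 = 360, which agrees with the stated 264 and 360 h. Leaving home stools aside, the gaps are 168–240 h and 264–336 h, 72 h each.

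**2. Effect of one endpoint.** Assumptions, not in the documents: constant fecal output of 1% of dose per 24 h (true gap content 3.0%) and a linear trapezoid between the two adjoining 24 h windows. With A1 and A2 the percentages of dose in those windows, the supplement is 72 × (A1/24 + A2/24)/2 = 1.5 × (A1 + A2).

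| A1, A2 | Supplement | Error against 3.0 |
|---|---|---|
| 1, 1 | 3.0 | 0 |
| 0, 1 | 1.5 | −50% |
| 2, 1 | 4.5 | +50% |
| 0, 2 | 3.0 | 0 |
| 0, 0 | 0 | −100% |
| 2, 2 | 6.0 | +100% |

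At 2% per 24 h every amount doubles.

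**3. Delivered or passed.** The table compares with output delivered to the gut during the gap. Fe counts what is passed. After a stool-less 144–168 h window the withheld 1% is passed inside the gap: 4.0% is passed and the rule gives 1.5%. If the stool-less day is the last of the gap, 2.0% is passed and the rule gives 4.5%, so the backlog is counted twice. Against the amount passed, the error is therefore 2.5 points rather than 1.5.

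**4. Spread.** Let p be the chance of at least one stool in a 24 h window (assumed). At constant output a window's content has mean 1 and variance 2(1 − p)/p. The average of two independent windows then has relative SD √((1 − p)/p): 23% at p = 0.95, 33% at 0.9, 50% at 0.8. Simulation that forces a stool by the third day gives 23%, 33%, 47%, and 65% at p = 0.63. The mean is 1.00 × true throughout. At least one endpoint is zero with probability 1 − p² = 19% at p = 0.9.

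Against the amount passed, the simulated error SD is 1.4, 2.0 and 2.5 points of 3.0 at p = 0.9, 0.8 and 0.67. Dividing by the time since the previous stool gives 0.5, 0.7 and 0.9, about a third.

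**5. Eligible subjects.** Averaging one stool a day does not guarantee one in every window: with Poisson counts of mean 1 per day, p = 1 − e⁻¹ = 0.63. Simulated subjects averaging 1.0–1.6 stools a day, with output 1% per 24 h at Day 8, a linear trapezoid and no home stools counted, gave an error SD of about 1.0–2.8 points of a true 2.4–3.0. The stool-to-stool denominator gave 0.3–0.9.

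**6. Home stools.** If all stools from the 48 h before admission count as measured, only 168–192 h and 264–288 h need filling. At p = 0.9 and constant output the relative SD falls from 33% to 19% of the 72 h amount. In points, it falls from 1.33 to 0.63 (10% of windows skipped, constant output) and from 2.87 to 1.54 (33% skipped, 72 h half-life). If instead home plus visit stool (192–264 h, up to 72 h of output) is divided by 24 h, the endpoint is inflated up to 72/24 = 3 times.

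**7. Integration rule.** With an assumed 2-day half-life and p = 0.9 the relative SD is 60% under a linear trapezoid, 44% under linear-up/log-down, and 17% with the stool-to-stool denominator under a linear trapezoid. Separately from stool timing, a linear trapezoid on this falling curve overstates the gap by 20% even with a stool every day (4% under linear-up/log-down). The stool-to-stool denominator does not remove that bias (mean 1.29 × true at p = 0.9, linear).

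**The case against.** The strongest reply has five parts.

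- **The formula has no fixed denominator.** A reader might infer that the SAP divides every fecal amount by 24 h. It divides by t_end − t_start. The 24 h follows from footnote k and holds in-house; for return visits the fecal interval is undefined. This stands as a correction, but the in-house endpoint is still affected.
- **The subjects are selected for regularity and constipation is managed.** This limits the effect without removing it. The criterion is an average, the measures start only after two days, and the SAP itself gives the absence of defecation as its example.
- **Home stools shorten the gap.** This stands and roughly halves the error, provided the SAP counts them, which it does not say.
- **The noise is assumed, not shown.** A reader might infer that the fecal supplement is mostly stool-timing noise. The documents give no stool frequency or late-excretion data. In the constant-output model the SD runs from 0% with a daily stool upward. It passes half the delivered amount only when p is below about 0.8, or half the passed amount at p of roughly 0.85–0.9 or below. What can be said is that timing can dominate.
- **Nothing turns on it.** A reader might infer that a shift across 90% recovery changes a conclusion. The 90% figure governs discharge and recall, not an SAP success criterion, and no hypothesis is tested. Interval amounts are also listed by subject, so a stool-less endpoint would be visible. All this stands, and it confines the point to precision.

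**Conclusion.** The concern holds as a matter of precision. Stated rules, not merely missing detail, turn a stool-less last in-house window into a rate of 0 and a one-day backlog stool into about twice the true rate. Either shifts a 72 h gap estimate by about 50%, or 1.5 points of dose, assuming 1% per 24 h, constant output and a linear trapezoid. Errors at the two ends can cancel, and stool timing adds little or no bias on average. With so few subjects, however, averaging gives little protection to a recalled subject's Fe(feces) and Fe(total).

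The effect does not arise if nobody is recalled, and how many will be is not known from the documents. Its size depends on stool frequency, the decline of excretion after Day 8, the integration rule and the treatment of home stools.

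**What to change.** In SAP 15.2.3, keep Ae/(t_end − t_start) for urine. For feces:

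1. Count stools collected at home before a return visit as measured excretion, and set the gap and t_start/t_end to match, so that up to 72 h of stool is never divided by 24 h.
2. Take the rate at each end of a gap as the radioactivity in the stool or stools divided by the time since the previous stool. Where that time is unknown, use a rate over several collection days.
3. Never use a stool-less window as a gap endpoint.
4. Name the AURC integration rule.

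The cost is a few SAP sentences and a small change to the SAS program. Collection times are already recorded. The time of the last uncollected stool before the first home stool is not, and the SAP already cites a final eCRF, so that time may have to be self-reported and will be slightly imprecise.

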16.0 Safety Analyses

16.1 Safety Variables

The following safety variables will be summarized:

- Adverse Events (AEs)
- Vital Signs
 - Supine Blood Pressure
 - Systolic Blood Pressure (SBP)
 - Diastolic Blood Pressure (DBP)
 - Pulse rate
 - Temporal temperature
 - Respiratory rate
- Electrocardiograms (ECG)
 - Heart Rate
 - PR Interval
 - QRS-Duration
 - QT Interval
 - QTc (Fridericia's) Interval
- Clinical Laboratory Evaluations
 - Clinical Chemistry
 - Hematology
 - Urinalysis
- Physical Examination

16.1.1 Adverse Events

All AE summaries will include only treatment emergent adverse events. Treatment-emergent adverse events (TEAE) are those which occur after the first dose of study drug.

A summary of the number of events, and the number and percentage of subjects reporting each TEAE, categorized by system organ class (SOC) and preferred term coded according to the MedDRA (Version 24.1) will be presented by treatment. Subjects will only be counted once within each SOC or preferred term. This summary will be provided for all TEAEs and for related TEAEs.

Summary tables will present the counts in descending order by SOC and preferred term (within a SOC) based on the number of subjects experiencing the event.

A summary of the number of events, and number and percentage of subjects reporting each TEAE, categorized by relationship to study drug as recorded on the eCRF, will be provided.

A summary of the number of events, and number and percentage of subjects reporting each TEAE, categorized by severity as recorded on eCRF, will also be provided.

A listing of adverse events leading to study discontinuation will be provided.

All adverse events (including non-treatment-emergent events) recorded on the eCRF will be listed.

The following missing data will be imputed as defined (for calculations only / will not be presented):

- Missing AE start and / or end times for the calculation of onset and duration will be assumed to be at 00:01 for a start time and 23:59 for end times. If the missing AE start time occurs at day of dosing, it will be set to one minute after dosing
- Missing AE start times for the determination of treatment emergence will be assumed to occur after treatment unless partial date documents the AE as happening prior to treatment
- Missing AE start date will be assumed to be after treatment for the determination of TEAE
- Missing AE severity or relationship will be assumed to be severe or related, respectively

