### 3.5.1.2.1 Adverse Events

AEs will be recorded from signing the ICF until completion of the follow-up visit. Any clinically significant observations, as determined by the Investigator, in results of clinical laboratory, 12-lead ECGs, vital signs, or physical examinations will be recorded as AEs.

A TEAE is defined as any event not present prior to administration of the study drug or any event already present that worsens in either severity or frequency following exposure to the study drug.

An AE that occurs prior to administration of the study drug will be considered a pretreatment AE.

At several time points before and after drug administration, subjects will be asked nonleading questions to determine the occurrence of AEs. Subjects will be asked in general terms about any AEs at regular intervals during the study. In addition, all AEs reported spontaneously during the course of the study will be recorded. All answers will be interpreted by the Investigator using the Medical Dictionary for Regulatory Activities (MedDRA; most recent version) for AEs and will be recorded in the eCRF as reported terms.

The severity of the AEs will be rated as mild, moderate, or severe; the relationship between the AEs and the study drug will be indicated as related or not related. Details on rating the severity of AEs and relationship to study treatment are given in Appendix 8.2.

Pregnancy of female partners of male subjects will be monitored along with follow-up, if warranted (see Appendix 8.3).

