##### 3.6.2.2.1 Adverse Events

A listing of all individual AEs will be provided. Summary tables of TEAEs will be presented by system organ class based on the MedDRA terminology list (preferred terms): 1 containing the number of TEAEs (frequency of occurrence, number of subjects experiencing the event) by treatment and 1 containing the number of drug-related TEAEs (frequency of occurrence, number of subjects experiencing the event) per treatment. Additional tables of total counts by treatment and relationship and by treatment and severity will be given.

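### The SAP's definition of a treatment-emergent adverse event omits the protocol's clause on worsening of pre-existing events and does not declare the change; two minor PK reporting items are also dropped undeclared

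*SAP*

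**What the plan says.** **Adverse events.** Protocol 3.5.1.2.1 treats an event as treatment-emergent if it was absent before dosing, and also covers "any event already present that worsens in either severity or frequency following exposure to the study drug". The same section starts collection at consent: "AEs will be recorded from signing the ICF until completion of the follow-up visit". The protocol's statistical section (3.6.2.2.1) relies on that term: "Summary tables of TEAEs will be presented by system organ class based on the MedDRA terminology list".

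SAP 16.1.1 has a single limb: "Treatment-emergent adverse events (TEAE) are those which occur after the first dose of study drug". It adds that "All AE summaries will include only treatment emergent adverse events". Its missing-data rules for treatment emergence look only at when the event started: a missing start time counts as post-dose "unless partial date documents the AE as happening prior to treatment", and "Missing AE start date will be assumed to be after treatment for the determination of TEAE".

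**PK statistics.** The protocol synopsis (Statistical Methods) asks for n, number missing (m), geometric mean, geometric CV, mean, CV, SD, median, minimum and maximum. SAP 15.2.2 names number of subjects, arithmetic mean, SD and CV, with the median alone for tmax. The SAP's general default (8.1.3) adds median, minimum and maximum, but neither section has geometric statistics or m.

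**Blood to plasma ratio.** The synopsis (Variables) lists whole-blood to plasma ratios for total radioactivity, qualified by 'as appropriate' and with no stated basis. No SAP parameter table or output list contains one.

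**Declared changes.** SAP 2.0 says that substantial differences from the protocol will be identified. SAP 6.1 declares two: one integrated SAP, and three subjects being sufficient.

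**The concern.** Safety and tolerability form the secondary objective, and the in-text adverse event outputs in SAP Appendix 3 are all TEAE tables. If the rule that is programmed is narrower than the protocol's, an event that the protocol regards as treatment-emergent can be missing from every adverse event table in the report.

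The omission would also be hard to notice later. The SAP says that it supersedes the protocol's statistical considerations. Protocol 3.6.2 asks the study report to describe deviations from the SAPs, and applying SAP 16.1.1 as written is not such a deviation. SAP 6.1 is the natural place to declare the change, and it is silent.

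The two PK items matter less. Log-scale summaries named in the synopsis would not be printed, and a variable named there has no stated place in the planned outputs.

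**Working it through.** The study is descriptive, with no power or alpha to reproduce. The check is a comparison of texts plus some simple sizing.

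**1. Does the SAP rule exclude worsened events?** Take a mild event that starts on Day -1 and becomes moderate after dosing.

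- Protocol 3.5.1.2.1: it was already present and worsened in severity, so it is a TEAE.
- SAP 16.1.1, one eCRF record with its pre-dose start: it did not first occur after dosing, so it is not a TEAE and enters no summary.
- SAP 16.1.1, worsening entered as a new record with a post-dose start: it is a TEAE, and the documents agree.

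The result depends on the eCRF convention, which neither document states. The start-based imputation rules suggest that emergence will be decided by start date and time.

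**2. Can pre-dose events exist?** Recording begins at consent, and screening can begin on Day -21. With no Day 0, Day -21 to Day 1 is 21 days, so the pre-dose window is up to about 21 days.

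**3. Size in a table.** One subject is 1/n of the denominator:

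- 4 dosed: 1/4 = 25 percentage points
- 5 dosed: 1/5 = 20
- 6 dosed: 1/6 = 17

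These are upper limits per affected subject. Because "Subjects will only be counted once within each SOC or preferred term", the change is 0 if that subject already has a TEAE in the row.

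**4. Arithmetic versus geometric mean.** The documents give no CV, so I assume log-normal data with CV 30%, 50% or 80%. For a sample of size n, the expected ratio of arithmetic to geometric mean is exp[s²(1 − 1/n)/2], with s² = ln(1 + CV²). At n = 4 the exponent is 0.375 × s²:

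| Assumed CV | s² | Expected ratio |
|---|---|---|
| 30% | ln 1.09 = 0.0862 | 1.033 |
| 50% | ln 1.25 = 0.2231 | 1.087 |
| 80% | ln 1.64 = 0.4947 | 1.204 |

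Simulation with 400,000 samples per CV gave the same three ratios. Neither mean is wrong; the table shows only how far the two can differ.

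**5. Data behind the ratio.** Table 1, footnote i, of the protocol schedule gives 15 post-dose times to 96 h (0.25, 0.5, 1, 1.5, 2, 3, 5, 8, 12, 16, 24, 36, 48, 72, 96). In 4 subjects that is up to 15 × 4 = 60 blood and plasma pairs. Adding 120, 144, 168, 264 and 360 h gives 20 times and up to 80 pairs, if all are quantifiable. Twenty plus predose is 21, which matches the 21 samples in protocol Table 3.

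**6. Is the ratio assigned elsewhere?** SAP Table 2 assigns AUC0-t to the integrated PK report. It makes no such assignment for the ratio.

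**The case against.** The strongest reply is that the consequence of the TEAE wording depends on an eCRF that is not available here. The SAP says it is to be read together with the protocol and eCRF, and if worsening opens a new record nothing is lost. The study has one open-label arm, about four healthy subjects and no hypothesis test. All adverse events, including non-emergent ones, are listed, and a listing for so few people is easily read. SAEs and events leading to discontinuation have their own listings. The missing-date rules lean towards counting an event as emergent. The 25-point figure reflects the sample size and says nothing about likelihood. It can also be argued that the SAP supersedes only statistical considerations, so the definition in the protocol's measurement section still stands.

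Most of this stands as a limit on the impact. It does not remove the conflict: there are two definitions, and the SAP's is the one attached to the tables. If the protocol definition is meant to govern, SAP 16.1.1 should say so.

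On the PK items, the SAP promises to identify only substantial differences, individual values are tabulated so that the missing statistics can be derived, and samples without a result are marked. Protocol Table 4 itself omits the ratio, and protocol 3.5.3.1 leaves the complete parameter list to the PK SAP. SAP 8.1.1 has a rounding rule for ratios in general, but it defines no blood to plasma ratio. Plasma and blood radioactivity are tabulated and plotted together. These points justify calling both items minor.

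**Conclusion.** The concern holds and should be corrected. As written, SAP 16.1.1 is narrower than the protocol's TEAE definition, and SAP 6.1 does not declare the difference. Confidence in the textual conflict is high. Its effect is conditional: a protocol-defined TEAE drops out of the summary tables only if worsening is kept inside the original pre-dose record. The two PK omissions are real but presentational, and nothing is lost that could not be derived from tabulated data. The points raised here are not a full comparison of the two documents.

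**What to change.** - **SAP 16.1.1:** add pre-existing events that worsen in severity or frequency after dosing to the TEAE definition, and state how worsening is recognised from the eCRF, for example as a new record with its own start date.
- **SAP 15.2.2:** add geometric mean, geometric CV and m for parameters such as Cmax and AUC, and confirm whether the median, minimum and maximum from SAP 8.1.3 apply.
- **SAP Table 2 and Appendix 4:** add the whole-blood to plasma ratio of total radioactivity with its basis (by time point, by AUC, or both), or name the separate report that will carry it.
- **SAP 6.1:** list, with a reason, any of these items deliberately not restored.

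The cost is SAP wording, a few summary rows and one derived variable from data already collected. No new samples or assays are needed.

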### **Study Schedule**

Screening	: Between Day -21 and Day -2.
Treatment period	: From Day -1 (admission) to approximately 96 hours after study drug administration (Day -1 up to afternoon Day 5) with possible extension (Day 6 to Day 8) as well as possible 24-hour visits (Day 11-12, Day 15-16).
Follow-up	: 30 days ( $\pm 2$ days) after the [  C]BTZ-043 dose.

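### SAP 16.1.1 counts an AE with a missing start as treatment-emergent even when its recorded end shows that it was over before dosing

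*SAP*

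**What the plan says.** SAP 16.1.1 defines the class first: "Treatment-emergent adverse events (TEAE) are those which occur after the first dose of study drug". It also fixes what is tabulated: "All AE summaries will include only treatment emergent adverse events". It then gives separate rules for missing data.

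- **Onset and duration.** For a missing start time on the dosing day: "If the missing AE start time occurs at day of dosing, it will be set to one minute after dosing".
- **Treatment emergence, start time missing.** The event is "assumed to occur after treatment unless partial date documents the AE as happening prior to treatment".
- **Treatment emergence, start date missing.** "Missing AE start date will be assumed to be after treatment for the determination of TEAE".
- **Severity or relationship missing.** The event is taken as severe or as related.

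None of these rules looks at the AE end date or end time. SAP 8.1.2 (Imputation) adds no such check.

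Protocol 3.5.1.2.1 says "AEs will be recorded from signing the ICF until completion of the follow-up visit" and "An AE that occurs prior to administration of the study drug will be considered a pretreatment AE". The protocol synopsis (Study Schedule) puts screening "Between Day -21 and Day -2", so events from as much as 21 days before dosing can be on file.

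**The concern.** The start-date rule is a reasonable conservative default when nothing is known about timing. It is not reasonable when the record shows that the event had ended before the drug was given. In that case the default protects against nothing and puts a known pre-dose event in the wrong class.

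The SAP applies the missing test elsewhere: SAP 13.0 (Concomitant Medications) uses an end date before first dose to class a medication as prior. AEs have no equivalent. SAP 2.0 says that the SAP supersedes the protocol's statistical considerations, and SAP 6.1 (Changes from Protocol) lists no change to AE classification. A programmer who follows the bullet as written would therefore flag the event as a TEAE.

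What is at stake is the accuracy of the AE tables that serve the secondary objective of safety and tolerability. In a study this small, one subject is a large share of any percentage.

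**Working it through.** The plan gives no figure on this point, so there is none to reproduce.

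**1. The start-date rule applied to test records** (dosing on Day 1). The last column adds one condition: not a TEAE if the recorded end is before dosing.

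| Start date | Recorded end | Rule as written | With end-date exception |
|---|---|---|---|
| missing | Day -3 | TEAE | pretreatment |
| missing | Day 5 | TEAE | TEAE |
| missing | missing | TEAE | TEAE |
| Day -5 | Day -3 | pretreatment | pretreatment |
| Day 2 | Day 3 | TEAE | TEAE |

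Only the first row changes. It is also the only row where the rule as written conflicts with the SAP's TEAE definition and the protocol's pretreatment definition.

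**2. The Day 1 case.** Protocol 3.4.6 places dosing between 08:00 and 11:00. As an illustration, take dosing at 09:00 and an AE dated Day 1 with no start time and a recorded end at 07:30.

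- Treatment emergence: a Day 1 date does not itself show onset before dosing, so the exception in the start-time bullet is not met and the event is a TEAE.
- Onset and duration: the imputed start is 09:01, so duration = 07:30 − 09:01 = −91 minutes.

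The misclassification comes from the treatment-emergence bullet. The negative duration is a by-product of the separate onset rule.

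**3. Size.** Inputs:

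- Each subject counts once per preferred term or system organ class (SAP 16.1.1).
- The denominator is the subjects exposed (SAP 8.1.3).
- Four subjects are planned, and two back-ups may also be dosed (SAP 5.0).

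Step in incidence for one misclassified subject = 100 × 1/n:

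- n = 4: 100/4 = 25.0 points
- n = 5: 100/5 = 20.0 points
- n = 6: 100/6 = 16.7 points

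The step applies only if the subject has no other TEAE in that term. The event count rises by 1 in any case.

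**4. Related-TEAE table.** The event enters it only if relationship is recorded as related, or is also missing and so defaults to related.

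**The case against.** The strongest reply is that the SAP never says in words that an event with a known pre-dose end is a TEAE. The section's own definition excludes it. The bullets are meant for events of unknown timing, and the start-time bullet already yields to evidence that the AE came before treatment. On this view the intent is clear and only the drafting is loose. The intent is plausible, and a partly missing start date that is clearly before dosing is arguably covered. But the exception is attached to start times, and the start-date bullet has none. When a definition and an unconditional operating rule disagree, the program follows the rule.

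The reply is right on frequency and visibility. The trigger needs a fully missing start date (or, on Day 1, a missing start time) together with a recorded pre-dose end, in 4 to 6 subjects. Protocol 3.7 provides for source verification where applicable and for missing data to be explained in the CSR. All AEs are listed, with original data (SAP 16.1.1 and 8.1.2), so a reader could spot the case. There is no comparator and no hypothesis test.

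A reader might infer three stronger things that the documents do not support:

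- **That the rule attributes the event to the drug.** TEAE status is about timing. Causality is a separate assessment, and Protocol 8.2.1 ties a related event to a reasonable time sequence after dosing.
- **That the shift is always 25 points.** It depends on the number dosed and on the subject's other TEAEs.
- **That negative durations would distort reported results.** SAP Appendices 3 and 4 plan no table of AE onset or duration. An impossible value met in programming would also be queried with the Data Manager under SAP 7.2.

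**Conclusion.** The point holds as a rule that gives the wrong class in an identifiable case. As written, SAP 16.1.1 makes an AE treatment-emergent when its start date is fully missing, even if its end is recorded before dosing. The start-time bullet does the same to a Day 1 AE whose recorded end time is before dosing.

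Each occurrence adds one false event to the TEAE tables. For a subject with no other TEAE in that preferred term, incidence rises by 25.0, 20.0 or 16.7 points with 4, 5 or 6 dosed.

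This rests on a literal reading of the bullets and on such a record staying unresolved at database lock. The documents do not say how often start dates will be missing; the case is probably rare. The primary mass-balance objective is not affected.

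**What to change.** Add to both treatment-emergence bullets in SAP 16.1.1: *unless the recorded AE end date (or, on Day 1, end time) is before dosing, in which case the AE is pretreatment.* In the onset and duration bullet, state that an imputed Day 1 start time may not be later than the recorded end time. Keep the conservative default for all other cases, including events with both dates missing and events that end after dosing.

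The cost is a short addition to the SAP and one condition, plus the Day 1 limit, in the adverse-event dataset program. No event of uncertain timing leaves the TEAE tables. If the SAP is not reissued, SAP 2.0 allows the change to be identified in the CSR instead.
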